## 5.5. Concomitant Therapies

During Visit 1 (Screening), the investigator or designee will question the subject to ensure they have not used any excluded therapies. Concomitant therapies are any new or existing therapies used from Screening (Visit 1) until Day 197 (Visit 11). Concomitant therapies include drug (e.g.

prescription and over the counter [OTC]), and non-drug modalities (e.g., chiropractic, physical therapy).

### **5.5.1. Permitted Concomitant Therapies**

Subjects will be allowed to use therapies not restricted by the protocol if they have been on a stable dose prior to study entry. Vitamins, minerals, and dietary supplements are permitted while on study if the subject has been on a stable dose prior to study entry and, in the opinion of the Investigator, will not affect the safety or efficacy of the subject during the study.

Topical products such as make up and moisturizers used consistently prior to study enrollment on the face and eyebrow area should be reviewed by the Investigator and are permitted if, in the Investigator's opinion, they will not affect the assessments of the subject during the study.

Topical therapies such as topical corticosteroids are permitted if they are not applied on or near the eyebrow area. Inhaled or intranasal corticosteroids are allowed in the study.

Prior permitted concomitant medications taken within 30 days of beginning treatment with study medication will be documented in the subject's source document and eCRF. In addition, any new permitted medications administered during protocol treatment and through Day 197 (Visit 11) will be documented in the subject's source document and eCRF.

### **5.5.2. Prohibited therapies**

Any medication or over-the-counter product known to affect hair growth is prohibited throughout the study period. Any prescription topical retinoids, over-the-counter topical products containing retinol, alpha hydroxy acids (e.g. glycolic, lactic acids) and beta hydroxy acids (e.g. salicylic acid) or cosmetic procedures applied to or in close proximity around the eyebrow area that in the opinion of the investigator may affect the safety or efficacy of the subject are prohibited throughout the study. New eyebrow tattooing, microblading, or piercing is not allowed during the study. During this study, subjects are prohibited from using therapies listed in the exclusion criteria. The investigator should notify the Medical Monitor, if any prohibited therapies are required to ensure subject safety.

## **5.6. Subject Discontinuation from the Study**

Subjects will be informed that they are free to withdraw from the study at any time and for any reason. The Investigator may remove a subject from the study if, in the Investigator's opinion, it is not in the best interest of the subject to continue the study. Examples of other reasons subjects may be discontinued from the study are: a change in compliance with an inclusion or exclusion criterion, occurrence of AEs, occurrence of pregnancy, or use of a prohibited therapy. Notification of discontinuation will immediately (within 24 hours) be made to the Aclaris Therapeutics, Inc. study monitor.

In case of premature discontinuation of study participation, efforts will be made to perform all final study day assessments. The date the subject is withdrawn from the study and the reason for discontinuation will be recorded in the subject's source documents and on his/her case report forms (eCRFs). All withdrawn subjects with ongoing AEs will be followed as specified in section 8.2.1 of this protocol.

The study may be discontinued at the discretion of Aclaris Therapeutics, Inc. Some examples of reasons for discontinuation are the occurrence of the following:

- Increased frequency, severity or duration of known AEs
- Medical, business, regulatory or ethical reasons affecting the continued performance of the study
- Difficulties in the recruitment of subjects

### **5.7. Subject Identifier (SI)**

The investigator or designee will assign a unique five-digit subject identifier (SI) to each subject at Visit 1.

The SI format will be NN-NNN where the first 2 digits are the investigational center site number (using leading zeroes as appropriate). The final 3 digits are the subject number and must be assigned in ascending numerical order, without omitting or repeating any number, starting with 001. For example, the SI for the second subject that signs an informed consent at site number 01 would be 01-002.

The subject will be identified using the SI in all study documentation for the duration of the study.

### **5.8. Replacement Subjects**

Subject enrollment will continue until approximately 12 subjects meet all the entry criteria and apply study medication at Visit 2 (Baseline). Subjects who are enrolled and do not complete the study will not be replaced.

## **6. INVESTIGATIONAL PLAN**

### **6.1. Study Design**

This is an open-label proof of concept study in subjects with unilateral or bilateral loss of some or all eyebrow hair due to AA, AU or AT. Subjects will treat affected eyebrow(s) with ATI-50002 Topical Solution 0.46% twice-daily for 24 weeks and will have a 4-week post-treatment follow up visit.

## 6.2. Study Flow Chart

CONFIDENTIAL  
Page 24 of 57

Visit Number	1 Screening	2 Baseline	3	4	5	6	7	8	9	10	11	Protocol Section
Week	-4 to -1	0	1	2	4	8	12	16	20	24	28	
Day	-28 to 0	1	8	15	29	57	85	112	141	169	197	
No-treatment follow-up												6.6.6
Subject instructions	X	X	X	X	X	X	X	X	X	X		6.4
Concomitant therapies	X	X	X	X	X	X	X	X	X	X	X	5.5.1
Adverse events		X	X	X	X	X	X	X	X	X	X	8

### 6.3. Study Visits Description and Procedures

A written, signed informed consent form (ICF) must be obtained from each subject prior to performing any study related procedure (*i.e.*, physical examination, clinical laboratory sampling, urine pregnancy test, ECG, or photography).

#### 6.3.1. Visit 1/ Screening (Week -4 to 0)

At this visit, the investigator or designee will:

1. Review and explain the nature of the study to the subject, obtain the subject's signature on the appropriate approved ICF and provide a signed and dated copy to the subject.
2. Assign a SI to the subject.
3. Confirm the subject meets all inclusion criteria and no exclusion criteria.
4. Collect demographic and medical history information (including alopecia history).
5. Collect concomitant therapies information.
6. Perform a brief physical examination.
7. Measure vital signs (including Height & Weight at this visit only).
8. Conduct an ECG.
9. Send patient for clinical laboratory tests including serum pregnancy test (if subject is WOCBP).
10. Identify the affected areas of eyebrow(s). Affected area is defined as the area of the eyebrow hair loss identified at baseline.
11. Perform a Clinician Eyebrow Assessment (CEA); a grade of 0 is required for at least one eyebrow with at least 30% eyebrow loss for the subject to continue in the study. Note: the subject may have multiple patches of eyebrow hair loss, but at least one distinct patch must demonstrate a minimum hair loss of at least 30% (independent of any other patches).
12. Have the subject complete a Subject Eyebrow Assessment (SEA); a grade of 0 is required for at least one eyebrow with at least 30% eyebrow loss for the subject to continue in the study. Note: the subject may have multiple patches of eyebrow hair loss, but at least one distinct patch must demonstrate a minimum hair loss of at least 30% (independent of any other patches).
13. Review the study instructions with the subject.
14. Schedule Visit 2 as appropriate.

### 6.3.2. Visit 2/ Baseline (Day 1)

This visit must occur within 28 days after Visit 1.

Subsequent study visit dates must be scheduled based on the date of Visit 2.

This visit may not occur before the investigator reviews the Visit 1 clinical laboratory test results for all the measured analytes. For the subject to continue in the study all clinical laboratory test results must be within the range of normal for the laboratory or, if there are any abnormal results, they must be defined as not clinically significant (NCS) by the investigator. For WOCBP, the serum pregnancy test from Visit 1 must be negative for a subject to continue in the study.

The investigator must review the evaluator's interpretation of each subject's Visit 1 ECG prior to Baseline/Visit 2 and comment on the clinical significance of any result that is defined by the evaluator as abnormal. The subject must not continue in the study and apply study medication, if the Visit 1 ECG meets any of the Criteria in Exclusion Criterion 18).

At this visit, the investigator or designee will perform the following procedures PRIOR TO APPLICATION OF STUDY MEDICATION:

1. Subject should have clinical laboratory tests performed at the local laboratory on the same day as the visit.
2. Query the subject in a non-directive manner about any changes in her/his health since the previous visit and report changes on the appropriate form.
3. Query the subject about any changes in her/his concomitant therapies since the previous visit and report changes on the appropriate form.
4. Confirm the subject meets all inclusion criteria and no exclusion criteria.
5. Confirm the subject continues to comply with all study restrictions, is eligible to continue in the study and has followed all study instructions.
6. Measure vital signs.
7. Perform a urine pregnancy test for WOCBP; results must be negative for the subject to apply the first dose of study medication.
8. The investigator or designee will perform a CEA; a CEA grade of 0 in a distinct patch of at least 30% total unilateral eyebrow hair loss is required for the subject to apply the first dose of study medication. Note: the subject may have multiple patches of eyebrow hair loss, but at least one distinct patch must demonstrate a minimum hair loss of at least 30% (independent of any other patches).
9. Confirm subject is eligible to apply the first dose of study medication.
10. Discharge from the study subjects who are not eligible to apply the first dose of study medication.

For subjects who are eligible to apply the first dose of study medication the investigator or designee will perform the following procedures:

1. Have the subject complete a SEA; a SEA grade of 0 in a distinct patch with at least 30% total unilateral eyebrow hair loss is required for the subject to apply the first dose of study medication. Note: Subject may have multiple patches of eyebrow hair loss, but at least one distinct patch must demonstrate a minimum hair loss of at least 30% (independent of any other patches).
2. Have the subject complete the SES question.
3. Have the subject perform a pre-application Local Tolerability Assessment (LTA).
4. The Investigator or designee will perform a pre-application LTA.
5. Take standardized color photographs.
6. Conduct an ECG.
7. Dispense study medication to the subject.
8. An investigational staff member will instruct the subject on the proper study medication application technique and will observe the subject's first study medication application.
9. A staff member will monitor the subject for at least 20 minutes after the first study medication application completion time to detect any adverse events.
10. Have the subject perform a post-application LTA 10 ( $\pm 4$ ) minutes after the application completion time.
11. The investigator or designee will perform a post-application LTA 20 ( $\pm 4$ ) minutes after the application completion time.
12. Review the study instructions with the subject.
13. Schedule Visit 3 as appropriate.

### 6.3.3. Visits 3-9 (Weeks 1, 2, 4, 8, 12, 16 and 20)

These visits must occur on the following weeks after Visit 2:

- Visit 3, 1 week ( $\pm 4$  days)
- Visit 4, 2 weeks ( $\pm 4$  days)
- Visit 5, 4 weeks ( $\pm 4$  days)
- Visit 6, 8 weeks ( $\pm 4$  days)
- Visit 7, 12 weeks ( $\pm 4$  days)
- Visit 8, 16 weeks ( $\pm 4$  days)
- Visit 9, 20 weeks ( $\pm 4$  days)

At these visits, the investigator or designee will perform the following procedures:

1. Query the subject in a non-directive manner about any changes in her/his health since the previous visit and report all AEs on the appropriate form.
2. Query the subject about any changes in her/his concomitant therapies since the previous visit and report changes on the appropriate form.
3. Confirm the subject continues to comply with all study restrictions, is eligible to continue in the study and has followed all study instructions.
4. Measure vital signs.
5. **AT VISIT 7 ONLY**, send subject for clinical laboratory tests prior to the study visit (on the same day).
6. Have the subject perform a LTA.
7. The investigator or designee will perform a LTA.

CONFIDENTIAL  
Page 27 of 57

8. **AT VISITS 5-9 ONLY**, the investigator or designee will perform the CEA.
9. **AT VISITS 5-9 ONLY**, have the subject complete the SEA.
10. **AT VISITS 5-9**, perform a urine pregnancy test for WOCBP; results must be negative for the subject to continue in the study.
11. **AT VISIT 7 ONLY**, have the subject complete the SES.
12. **AT VISITS 5-9 ONLY**, take standardized photographs.
13. Dispense and/or collect study medication as appropriate.
14. Review the study instructions with the subject.
15. Schedule the next visit as appropriate.

#### **6.3.4. Visit 10 (Week 24)**

This visit must occur 24 weeks ( $\pm 4$  days) after Visit 2.

At this visit, the investigator or designee will perform the following procedures:

1. Query the subject in a non-directive manner about any changes in her/his health since the previous visit and report all AEs on the appropriate form.
2. Query the subject about any changes in her/his concomitant therapies since the previous visit and report changes on the appropriate form.
3. Confirm the subject continues to comply with all study restrictions and has followed all study instructions.
4. Measure vital signs.
5. Conduct an ECG.
6. Confirm subject had clinical laboratory tests prior to the visit (on the same day).
7. Perform a urine pregnancy test for WOCBP.
8. Have the subject perform a LTA.
9. The investigator or designee will perform a LTA.
10. The investigator or designee will perform the CEA.
11. Have the subject complete the SEA.
12. Have the subject complete the SES.
13. Collect all study medication.
14. Take standardized photographs.
15. Review the study instructions with the subject.
16. Schedule the next visit as appropriate.

#### **6.3.5. Visit 11 (Week 28)**

This visit must occur 28 weeks ( $\pm 4$  days) after Visit 2.

At this visit, the investigator or designee will perform the following procedures:

1. Query the subject in a non-directive manner about any changes in her/his health since the previous visit and report all AEs on the appropriate form.
2. Query the subject about any changes in her/his concomitant therapies since the previous visit and report changes on the appropriate form.
3. Confirm the subject continues to comply with all study restrictions and has followed all study instructions.

4. Conduct a brief physical examination.
5. Measure vital signs.
6. Conduct an ECG.
7. Confirm subject had clinical laboratory tests prior to visit (same day).
8. Perform a urine pregnancy test for WOCBP.
9. Have the subject perform a LTA.
10. The investigator or designee will perform a LTA.
11. The investigator or designee will perform the CEA.
12. Have the subject complete the SEA.
13. Have the subject complete the SES.
14. Take standardized photographs.
15. Discharge the subject from the study.

#### **6.4. Subject Instructions**

An investigational center staff member will dispense and review the Subject Instruction Sheet to each subject at Visit 2 through Visit 10 (see Section 14, Appendix A).

#### **6.5. STUDY DURATION**

The duration of study participation is anticipated to be a maximum of 233 days per subject. This includes the up to 28-day screening period, a 169-day treatment period and a 28 day no-treatment follow-up period. The final study visit (Visit 11) has a maximum allowable visit window of +4 days.

The study end date is the date of the last subject's last visit.

## 6.6. STUDY MEDICATIONS

### 6.6.1. Study medication identity

The study medication for this study is ATI-50002 Topical Solution 0.46%. The study medication is a clear, colorless to light pink solution. The inactive ingredients include: water, Transcutol P, propylene glycol, PEG400, dimethyl sulfoxide (DMSO), Kolliphor CS 20, benzyl alcohol, poloxamer 188, and povidone K30. The study medications must be stored in a secure area with limited access under appropriately controlled and monitored storage conditions.

Study Medication Information	
Study medication name	ATI-50002 Topical Solution 0.46%
Manufacturer	PMRS, Inc., Horsham, PA, USA
ATI-50002 concentration (%)	0.46
Pharmaceutical Form	Topical Solution
Container	Amber Glass Bottles, 30 ml with screw cap
Storage Conditions	59°F to 77°F (15°C to 25°C) protected from light, excessive heat, open flame and combustibles, out of direct sunlight and in a well-ventilated, dry area
Dose regimen	
Route	Topical
Frequency	Twice-daily application
Duration of administration	24 weeks
Other Supplies	Disposable applicators

### **6.6.2. Study medication packaging and labeling**

The study medication will be packaged in 30 ml amber glass bottles with tamper-resistant caps.

Study medication packaged in individual cartons, each with a unique number, will be provided to the investigational center for each subject. An adequate supply of study medication applicators will also be supplied. One bottle of study medication is sufficient for approximately 2 weeks of twice-daily applications.

Each study medication bottle will be labeled with a one-part label that remains attached to the bottle and shows at least the following:

- Protocol number
- ATI-50002 Topical Solution 0.46%
- Storage conditions
- Sponsor information
- Investigational drug warning
- Space to enter Subject Identifier

### **6.6.3. Method of treatment assignment**

This study is an open-label study and all subjects will receive ATI-50002 Topical Solution 0.46%.

### **6.6.4. Subject Eligibility to Receive Study Medication**

At Visit 2 the investigator or designee will determine if the subject is eligible to apply study medication. Eligibility requirements include, but are not limited to:

- The subject must not apply the first dose of study medication unless all the required clinical laboratory test results are within the range of normal for the laboratory, or, if there are any abnormal results, they must be defined as not clinically significant (NCS) by the investigator.
- For WOCBP, the serum pregnancy test from Visit 1 must be negative for the subject to continue in the study. Additionally, a urine pregnancy test at Visit 2 must be performed and found to be negative prior to application of the first dose of study medication.
- The subject must not apply study medication if the Visit 1 ECG meets any of the Criteria in Exclusion Criterion 18).

### **6.6.5. Dispensing and collecting study medication**

The study medications must be dispensed only to study subjects, only at the investigational center noted on the FDA Form-1572 and only by authorized personnel as required by applicable regulations, guidelines and protocol.

At Visit 2, after a subject is confirmed to be eligible to apply study medication, research center staff will assign an initial supply of three study medication bottles. Research center staff will record the SI on each bottle label.

CONFIDENTIAL  
Page 31 of 57

At Visits 3-9, examine the subject's dispensed study medication bottles, collect bottles that are empty or do not contain sufficient volume of study medication available for use with the applicator, and dispense additional bottles as appropriate following the instructions above.

At Visit 10, collect all dispensed study medication bottles.

Dispense a packet of study medication applicators to the subject each time a study medication bottle is dispensed. It is not necessary to collect unused applicators from the subject.

The investigational center staff should make every effort to obtain all dispensed study medication from each subject. Two documented telephone contacts with the subject followed by a registered letter to the subject constitute adequate follow-up efforts. If these efforts fail, the reason for the failure must be noted on the appropriate study medication inventory eCRF and in the subject's source documentation.

#### **6.6.6. Study medication application**

The study medications are for external, topical use on the eyebrows on the appropriate study subject only.

At Visit 2, the staff member will instruct the subject on the proper application technique as detailed in Section 14 and observe the subject's first study medication application. The staff member should record the time that the subject completes the first study medication application. Monitor the subject for adverse events for at least 20 minutes after the application completion time.

#### **6.6.7. Dose compliance record**

The subject will be given an application calendar to record study medication applications. At every post-baseline study visit (Visit 3 and higher), an investigational center staff member will document the study medication compliance in the eCRF.

#### **6.6.8. Dose modification**

Subjects should not modify the study medication application procedure or frequency without the investigator's prior approval. All application modifications must be reported on the appropriate eCRF. If any meaningful study medication intolerance or safety issue occurs, after consulting with the Aclaris Therapeutics, Inc. Medical Monitor (see page 1), the investigator or designee may direct the subject to modify the study medication application frequency. If the subject cannot perform the twice-daily application frequency to the affected eyebrow(s) for more than 4 consecutive days, the subject must be removed from the study.

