#### 7.2.4. Clinical laboratory sampling

Subjects will go to a local laboratory (to be determined) to have the clinical laboratory tests at Visits 1, 2, 7, 10 and 11. WOCBP will have urine pregnancy tests performed by the study staff at Visit 2, 5, 6, 7, 8, 9, 10 and 11. Approximately 22.5ml of blood will be collected at Visit 1 and 10.5ml for each sample at Visits 2, 7, 10 and 11, a total of approximately 64.5ml per subject for the entire study. The following tests, at a minimum, will be conducted:

Chemistry Panel	Complete Blood Count
Albumin	Hematocrit
Alkaline phosphatase	Hemoglobin
Alanine aminotransferase (ALT)	Platelet count
Aspartate aminotransferase (AST)	Red blood cell morphology
Blood urea nitrogen (BUN)	Red blood cell count
Bicarbonate	White blood cell count
Calcium	White blood cell differential
Chloride	% & absolute
Creatinine	Basophils
Glucose	Eosinophils
Lactate dehydrogenase (LDH)	Lymphocytes
Phosphorus	Monocytes
Potassium	Neutrophils
Sodium	
Total bilirubin	Complete Urinalysis
Total protein	
Uric acid	
Total cholesterol, LDL, HDL	
Triglycerides	

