## 8.2.4. Study Medication Interruption and Discontinuation

### 8.2.4.1 Study Medication Interruption

Treatment with ATI-50002 Topical Solution should be temporarily interrupted in the event of severe adverse events considered related to ATI-50002, or in the event of one or more of the abnormal laboratory values in Table 1.

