**Table 1: Study Medication Interruption Criteria**

Laboratory Test	Interrupt Study Medication if:	Resume Study Medication if:
WBC count	< 2 x 10  /L	≥ 2.5 x 10  /L
ANC	< 1 x 10  /L	≥ 1.5 x 10  /L
Lymphocyte count	< 0.5 x 10  /L	≥ 0.75 x 10  /L
Platelet count	< 75 x 10  /L	≥ 100 x 10  /L
Hemoglobin	< 8 g/dL or decrease > 2 g/dL	≥ 10 g/dL
AST or ALT	> 3 x ULN	< 2 x ULN or within 20% of baseline values
Serum creatinine	>2 x ULN	<1.5 x ULN or within 10% of baseline value

If a subject has one or more of the abnormal laboratory values noted in Table 1, the investigator or designee upon receipt and review of the central laboratory report should instruct the subject to interrupt study medication applications. The investigator or designee should ask the subject about symptoms, concomitant illnesses and medications and repeat the test(s) as soon as possible. The Medical Monitor must be notified of dose interruptions due to SAEs considered related to study medication or laboratory abnormalities noted in Table 1.

If the retest confirms the abnormal laboratory value, then the study medication interruption should continue, followed by repeat testing once a week or sooner at the discretion of the investigator. The subject should be followed until the laboratory abnormality(s) return to normal or to baseline values. Application of study medication may be resumed upon resolution of the abnormal laboratory values to the levels specified in Table 1 above.

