### **8.2.4.2 Study Medication Discontinuation**

Study medication should be permanently discontinued in the event of any of the following:

- Severe infection requiring parenteral antimicrobial therapy or hospitalization
- Symptomatic herpes zoster
- Malignancy – except for non-melanoma skin cancer (e.g., squamous or basal cell carcinoma) not in or near the treatment area
- Anaphylactic or severe allergic reaction
- WBC Count:  $< 1 \times 10^9/L$  or second occurrence of  $< 2 \times 10^9/L$
- ANC:  $< 0.5 \times 10^9/L$  or second occurrence of  $< 1 \times 10^9/L$
- Lymphocyte count:  $< 0.3 \times 10^9/L$  or second occurrence of  $< 0.5 \times 10^9/L$
- Platelet count:  $< 50 \times 10^9/L$  or second event of  $< 75 \times 10^9/L$  - in each case, value should be confirmed by retesting before treatment discontinuation
- Hemoglobin:  $< 6.5 \text{ g/dL}$  or second occurrence of  $< 8 \text{ g/dL}$  - in each case, value should be confirmed by retesting before treatment discontinuation
- AST or ALT:
  - $> 5 \times \text{ULN}$  persisting for 1 week of study medication interruption or second event of  $> 5 \times \text{ULN}$
  - $> 3 \times \text{ULN}$  with total bilirubin  $> 2 \times \text{ULN}$  or symptoms of hepatocellular injury [fatigue, nausea, vomiting, right upper quadrant pain or tenderness, fever, rash and/ or eosinophilia ( $> 5\%$ )].
- Serum creatinine:  $> 2 \times \text{ULN}$  persisting for  $> 2$  weeks of treatment discontinuation or second occurrence of  $> 2 \times \text{ULN}$

The continued treatment of subjects who experience other serious or severe adverse events considered related to study treatment should be discussed with the Sponsor's medical monitor.

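### The 4-day removal rule in Section 6.6.8 conflicts with the temporary treatment interruptions ordered in Section 8.2.4

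*Combined protocol and SAP*

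**What the plan says.** Section 6.6.8 (Dose modification) lets the investigator, after consulting the Medical Monitor, change the application frequency for intolerance or a safety issue. Its next sentence says that if the subject cannot keep to twice-daily application "for more than 4 consecutive days, the subject must be removed from the study". It states no exception and does not refer to Section 8.2.4.

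Section 8.2.4.1 says treatment "should be temporarily interrupted in the event of severe adverse events considered related to ATI-50002", or for any laboratory value listed in Table 1. If a retest confirms the value, "the study medication interruption should continue, followed by repeat testing once a week or sooner at the discretion of the investigator". It then says: "Application of study medication may be resumed upon resolution of the abnormal laboratory values to the levels specified in Table 1 above". No maximum length of interruption is given.

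Section 8.2.4.2 lists the criteria for stopping permanently:

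- AST or ALT above 5 x ULN "persisting for 1 week of study medication interruption or second event of" that level.
- Creatinine above 2 x ULN persisting for more than 2 "weeks of treatment discontinuation or second occurrence of" that level.
- For the blood counts and hemoglobin, a more extreme value or a second occurrence of a low value.
- For remaining related events, the sponsor's medical monitor is to be consulted: "The continued treatment of subjects who experience other serious or severe adverse events considered related to study treatment should be discussed".

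Three further provisions determine the consequence. Section 5.8 does not replace subjects who fail to complete. Section 10.1 bases every efficacy summary on a per-protocol set that needs both Baseline and Visit 10 efficacy data. Section 5.6 asks sites to try to complete the final-day assessments when a subject leaves early, but does not say that these count as Visit 10.

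**The concern.** The two sections give different instructions for the same subject. Someone held off drug under 8.2.4.1 for a fifth day is, under 6.6.8, to be removed from the study; under 8.2.4.1 the same person is to be retested and may restart. The permanent-stop criteria in 8.2.4.2 make sense only if subjects stay in beyond day 4 and, for the second-occurrence criteria, only if they have resumed.

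Efficacy information in a very small study is at stake. A site that follows 6.6.8 loses a subject who might have recovered, restarted and been assessed at Visit 10. A site that follows 8.2.4 departs from a mandatory instruction, and the per-protocol set excludes major protocol violations, a term the protocol does not define. The two rules could also be applied differently at different sites.

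**Working it through.** The study has no power calculation (Section 10.2), so there is no planned figure to reproduce. The check compares the 4-day limit with the periods in 8.2.4, then works out when removal would fall.

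**Durations side by side**

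| Provision | Time off drug | Longer than 4 days? |
|---|---|---|
| 6.6.8 removal | more than 4 days, so triggered on the fifth day | – |
| 8.2.4.1 retest cycle after confirmation | 7 days, or sooner | yes, unless retested early |
| 8.2.4.2 AST/ALT > 5 x ULN | 1 week = 7 days | yes |
| 8.2.4.2 creatinine > 2 x ULN | more than 2 weeks = more than 14 days | yes |
| Other Table 1 tests; AST/ALT 3–5 x ULN without raised bilirubin or symptoms | no limit stated | can be |

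Read literally, 6.6.8 acts before any of the steps with a stated period can finish. An interruption that ends within 4 days creates no conflict.

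**Where the weekly retest falls.** Assumption: the confirming retest is on day 1 to 3 off drug. The next weekly retest is then on day 1 + 7 = 8 to day 3 + 7 = 10. Removal is triggered on day 5, so that retest comes 8 − 5 = 3 to 10 − 5 = 5 days too late. Retesting sooner is allowed, but helps only if recovery is shown within 4 days.

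**When removal would happen.** Section 7.2.4 sends subjects "to have the clinical laboratory tests at Visits 1, 2, 7, 10 and 11", so Visit 7 (Day 85) is the only scheduled draw between Baseline and end of treatment (Visit 10, Day 169). Assumption: the drug is stopped 1 to 5 days after the draw.

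- First day off drug: 85 + 1 = Day 86 to 85 + 5 = Day 90.
- Fifth day off drug: 86 + 4 = Day 90 to 90 + 4 = Day 94.
- Time left to Visit 10: 169 − 94 = 75 to 169 − 90 = 79 days.
- With the Visit 7 window of ±4 days (Day 81 to 89) and Visit 10 kept at Day 169: the fifth day off is 81 + 1 + 4 = Day 86 to 89 + 5 + 4 = Day 98, which leaves 169 − 98 = 71 to 169 − 86 = 83 days.

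A subject removed at that point would have had 10 weeks or more in which to recover, resume and be assessed.

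**Size of each loss.** Taking the planned number as 12: 1/12 = 8.3%, and 12 − 1 = 11 subjects at most remain in the efficacy set.

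**Frequency.** The documents give no interruption rate and none is assumed. Section 3.1 reports no clinically significant laboratory abnormalities in the Phase 1 study of the oral prodrug in healthy volunteers, which suggests that Table 1 interruptions will be uncommon. Severe related adverse events are not tied to Visit 7 and could arise at any time.

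**The case against.** The strongest reply is that no conflict was intended. Section 6.6.8 concerns changes in application frequency. Section 8.2.4 is a separate, more specific section on stopping the drug, with its own triggers and restart levels. A subject told to stop is not obviously one who cannot perform the regimen, and the specific section would ordinarily govern. That is probably the intention. But the protocol does not say so, and the removal rule directly follows a sentence about intolerance and safety issues, so a site could reasonably apply it to a safety hold. The wording gives no help: 6.6.8 uses mandatory language, while 8.2.4.1 says what should or may be done.

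A second reply is that oversight would catch inconsistent handling. There are only 1 to 2 sites, the Medical Monitor must be told of Table 1 interruptions, and safety is reviewed monthly. This makes divergence between sites less likely, but it does not tell the Medical Monitor which rule to apply.

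Third, the adverse-event case is weaker than the laboratory case, because no restart criterion is given for severe related events and continuation is a matter for discussion. That stands. The conflict there is between automatic removal and a case-by-case decision, not between removal and a defined right to resume.

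Fourth, the practical effect is small. Triggers are few, Table 1 values must be repeated as soon as possible, the analysis is descriptive, and no safety action is blocked. All of this is accepted. It limits how often the problem will arise, not what happens when it does. Baseline blood is drawn on the day of first dosing, so a Table 1 value from that sample might also come to light after treatment starts. The timing above does not cover that case.

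**Conclusion.** The concern holds. Section 6.6.8 as written requires removal on the fifth consecutive day without twice-daily dosing, while Section 8.2.4 orders interruptions that can properly last longer and lets subjects restart. Nothing in the protocol ranks the two.

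Each subject caught by this is about 8.3% of the planned sample, is not replaced, and would normally drop out of every efficacy summary. The subject's data would still be presented with those of all treated subjects. For a value found at Visit 7, removal would come 75 to 79 days before Visit 10, or 71 to 83 with the visit window. These timings rest on the assumed 1-to-5-day lag, and the retest comparison rests on the assumed confirming day. The conflict in the text depends on neither.

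The expected number of affected subjects cannot be estimated from the documents and is probably low. The point should still be fixed, because it is a direct contradiction in a study of about 12 subjects and the remedy is nearly free.

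**What to change.** Add two sentences to Section 6.6.8:

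> This 4-day removal rule does not apply to interruptions ordered under 8.2.4.1, which are governed by Section 8.2.4. These subjects continue scheduled visits during the interruption.

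The removal rule stays as it is for all other subjects. The sponsor may also set a maximum interruption length, which would deal with the possibility of a subject reaching Visit 10 after many weeks off drug.

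The cost is a short wording amendment. It adds no subjects, and no visits or procedures beyond those already scheduled.
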